**NCT04455035**

**Version Date: 07/16/2020**

**Protocol Title:** DynaCleft® Effects on Soft Tissues and on Quality of Life for Incomplete Unilateral Cleft Lip Infants

**Principal Investigator:** [name], D.D.S.

**Co-Investigators:** [name], D.D.S., Ph.D. and [name].

**Study Coordinator:** [name] and [name]

**Population:** Prospective study of 10 infants with non-syndromic unilateral incomplete cleft lip; retrospective chart review of infants with non-syndromic unilateral incomplete cleft lip without any presurgical interventions

**Number of Sites:** University of Texas Health Science Center at Houston (UTHealth) Advanced Education in Pediatric Dentistry and UTHealth Texas Cleft-Craniofacial Clinic

**Study Duration:** Two Years

**Subject Duration:** Prospective study – four months

---

### General Information

This prospective study will investigate soft tissue changes of the DynaCleft® + Nasal Elevator system (CranioRehab, Denver, CO) on infants with non-syndromic incomplete unilateral cleft lip. The retrospective aspect of the study will examine records of infants who had or will have surgery without presurgical interventions and will provide as the control group. A comparison will be performed to analyze the effectiveness of DynaCleft® on soft tissues and on the quality of life for these infants and that of their families. Factors such as general physical appearances, overall development, behavioral differences, feeding improvements, and social functions will be evaluated. The study aims to use these collected data to establish the effectiveness of DynaCleft® for orofacial clefts at a university-based postdoctoral pediatric dentistry clinic.

### Background Information

- Cleft lip and palate is globally the most common form of congenital craniofacial anomalies[1]. It is generally reported to affect approximately 1 in 700 live births[2] and may be isolated or associated with a syndrome. Children born with clefts are faced with many complicated issues that need to be addressed to ensure successful rehabilitation. A combination of factors such as functional, psychological, and sociological issues make this a challenging condition overall to manage. It has also been reported that this anomaly decreases the quality of life of the infant and that of their families due to the long road of costly operations and life adjustments[1].

IRB NUMBER: HSC-DB-20-0311

- Even a mild incomplete cleft lip without involvement of the palate can produce significant nasal deformities. These deformities include separated lip segments, widen nostril base, flattened nasal tip, flared alar rim, rotated premaxilla, deviated and deficient columella[3].
- Due to the complexity of this craniofacial birth defect, it has been found that early interventions prior to surgery may achieve improved esthetic and functional outcomes. Nasal, lip, and maxillary tissue can be expanded and malpositioned structures can be guided into a more anatomical position with presurgical orthopedics. This may allow for less invasive surgeries by minimizing the deformities[4]. This movement is facilitated by circulating maternal estrogens that are present in the first month or two of life. Presurgical cleft orthodontics take advantage of these estrogens as they increase hyaluronic acid in the tissue, causing greater pliability and plasticity, in the infant cartilage for recontouring[3]. Cheiloplasty usually occurs within the first few months of life at approximately 3-6 months of age depending on severity of the cleft lip. Palatal cleft surgical repair is often recommended later on between the 9-18 months of life.
- Throughout the past decades, many methods have been formulated to address orofacial clefts nonsurgically. DynaCleft® was introduced and approved by the Federal Drug Administration recently in 2013[4]. The kit consists of premade approximation tape with an elastomeric core that has been successfully used to bridge cleft segments and mold the upper lip. Tension from the band distributes passively over the cleft lip tissue and provides gentle guidance. A nasal stent is suspended from the forehead by an adhesive to support and reshape the developing affected nasal tissues prior to surgical repair. Parents are then instructed to continue replacing the tape with take home instructions up to the date of surgery[5].
- When compared with the widely accepted nasoalveolar molding technique (NAM) developed by Grayson in 1993[4], DynaCleft® showed equivocal results in bridging cleft lip segments closer in proximity, reducing palatal cleft width distance, decreasing nostril width while increasing its height, and improving the columellar angle[5] in infants with complete cleft lip and palate.
- Though studies have shown an overall efficacy of the DynaCleft® therapy, more research is necessary to establish the potential of this modality and to enhance its acceptance as a presurgical orthopedic molding alternative for infants with clefts[4, 6]. No studies have yet examined the effectiveness of DynaCleft® to treat patients with incomplete cleft lip, who due to the reduced severity of defect, do not receive presurgical infant orthopedic appliance therapy.

## Objectives

- The primary objective of this study is to examine the effectiveness of the DynaCleft® system on soft tissues of infants with unilateral incomplete cleft lip.
- The secondary objective of this study is to assess influences on quality of life for infants who underwent DynaCleft® and that of their families.

## Purpose

- Evaluate soft tissue changes of the oral and nasal regions in infants born with incomplete unilateral cleft lip from the initial time of examination with a craniofacial team to the time of

IRB NUMBER: HSC-DB-20-0311

cheiloplasty and to determine if the DynaCleft® + Nasal Elevator system (CranioRehab, Denver, CO) changes presurgical positioning of craniofacial soft tissues.

- Analyze the effect on quality of life for families that complete the prospective DynaCleft® study.

## **Outcome Measures (Endpoints) and Time Points**

### **Primary Outcome Measures:**

- Soft tissue changes as indicated by columellar angle measured from extraoral clinical photographs
  - Time points: initial time of examination with study team, time of surgery
  - Soft tissue changes as indicated by nostril width measured from extraoral clinical photographs
    - Time points: initial time of examination with study team, time of surgery
    - Soft tissue changes as indicated by nostril height measured from extraoral clinical photographs
      - Time points: initial time of examination with study team, time of surgery
      - Soft tissue changes as indicated by width of the cleft lip measured from extraoral clinical photographs
        - Time points: initial time of examination with study team, time of surgery

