**Prospective:**

- The study population for the prospective aspect will include recruited newborns with untreated unilateral incomplete cleft lip. Patients whose clefts are associated with a syndrome will be excluded. DynaCleft® + Nasal Elevator therapy will be discussed with parent(s) as a presurgical orthopedic option while awaiting primary cleft lip surgical repair that typically occurs between the ages of 3 to 6 months. Informed consent for participation in the study must be obtained from the patients' parents.
- Study duration will be up to three months of presurgical intervention (similar to the existing nasoalveolar molding NAM appliance protocols).
- Patients will be recruited by the Texas Cleft-Craniofacial team. ○ Infants that match the inclusion criteria will be invited to participate in this study.
- Photographs are to be taken at initial visit prior to presurgical intervention and later at completion of the DynaCleft® therapy immediately prior to lip surgery. Angles to be pictured are to include the standard anterior-posterior, profile, and worms-eye view.
- Linear measurements will be obtained with a ruler and registered in millimeters. A goniometer will be used to measure angles.
- The parents of infants enrolled in the DynaCleft® study will be asked to complete an Infant and New Parent Quality of Life survey at the initial and final visits. Components from this survey were adopted from the Infant and Toddler Quality of Life Questionnaire and the CDC Breastfeeding and Infant Practices Questionnaire (see attachments).

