**Prospective:**

- One evaluator will obtain all photographs to be evaluated in this study, examine Electronic Health Records, and collect necessary data and measurements onto a password protected Microsoft Excel Spreadsheet. Measurements to be recorded may include columellar angles, nostril width, nostril height, width of the lip cleft, etc. While most of the information can be gathered directly from the photographs, some factors may require calculations such as soft tissue ratios if need be. The primary investigator will be blinded to whether or not subject has participated in the DynaCleft® study. Data are to be measured twice and results compared to account for accuracy. Participants are identified on the spreadsheet solely by an assigned code. Factors to be recorded will also include general biographical and physical information (age, gender, weight, etc.), duration of treatment and compliance of caregivers.
- Interaction with

IRB NUMBER: HSC-DB-20-0311

participants in the DynaCleft® study will involve one monthly visit up until date of surgery, usually between 3 to 6 months of age. Each appointment is estimated to be

an hour long to allow for assessment of the orthopedic, recording of information, and addressment of any concerns. The initial and last visits may require more time due to obtainment of necessary photographs. Participants will be required to receive DynaCleft® treatment for at least 2 months before lip surgery to qualify. Additionally, parents of infants with incomplete unilateral cleft lip that choose not to use the DynaCleft® + Nasal Elevator system but are willing to complete the infant quality of life assessment at time of surgery will be allowed to complete the survey. All images obtained in this study will be stored in a password protected and encrypted computer. Prospective patient images will be stored in the Electronic Health Record. Images will be de-identified.

- Parents will be asked to complete the Infant and New Parent Quality of Life questionnaire at both the initial visit and date of surgery.

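### Nostril outcomes are raw millimetre changes and the columellar angle is not coded by cleft side, so growth in nostril height counts as improvement in the paired test and correction cannot be told from possible over-correction.

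*Combined protocol and SAP*

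**What the plan says.** Primary Outcome Measures lists four outcomes, all worded as change between the initial examination and surgery. Three matter here: "Soft tissue changes as indicated by columellar angle measured from extraoral clinical photographs", "Soft tissue changes as indicated by nostril width measured from extraoral clinical photographs" and "Soft tissue changes as indicated by nostril height measured from extraoral clinical photographs". The fourth is the width of the cleft lip.

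On scale and instrument, Study Design (Prospective) says "Linear measurements will be obtained with a ruler and registered in millimeters" and "A goniometer will be used to measure angles". The retrospective part uses the same method. Study Procedures (Prospective) adds that "some factors may require calculations such as soft tissue ratios if need be", without defining a ratio or tying one to an outcome.

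The document gives no reference line for the angle, no sign rule by cleft side, no statement of which nostril is measured, no target and no direction of success. The only directional wording is in Background Information, about a cited study in complete clefts: "decreasing nostril width while increasing its height, and improving the columellar angle". For the angle, that does not say which way is better.

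Statistics plans a paired t-test within patients and a comparison with untreated controls by a test to be chosen later. Study Design describes the primary outcome as a before-and-after comparison of photographs.

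**The concern.** Background Information states the general aim of this kind of therapy: "malpositioned structures can be guided into a more anatomical position with presurgical orthopedics". A raw change score has no anatomical target, which raises three problems.

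- **Growth.** Infants grow between the two photographs. If nostril height grows, raw height moves in the direction that Background Information treats as favourable. If width grows, it moves in the unfavourable direction. The paired test cannot separate either from a device effect.
- **Over-correction.** If a nostril were raised past the normal side, raw change would score this as more benefit although symmetry had worsened.
- **Side of cleft.** Left and right clefts are both eligible, and columellar deviation is a mirror-image deformity. Against one fixed axis, equal corrections on the two sides carry opposite signs.

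At stake is whether a significant change in nostril height, or a null result for the angle, can be interpreted at all.

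**Working it through.** **Inputs from the plan.** 10 prospective infants; significance at P below 0.05 (two-sided assumed, as sidedness is not stated). Age at lip repair is 3-4 months for controls (Study Population, Retrospective) and 3-6 months for device infants (Study Design and Study Procedures, Prospective).

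**Assumed inputs.** Effect sizes, SDs, growth rates, left/right shares and nostril sizes are not in the documents; neither is the number of controls, taken as 10. The plan gives no power figure to reproduce.

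**1. Growth in the paired test, no device effect.** Noncentral t with 9 degrees of freedom and noncentrality d × √10, where d is mean growth in height divided by the SD of change.

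| Growth d (SD) | Chance of a significant paired test |
|---|---|
| 0.5 | 29% |
| 1.0 | 80% |
| 1.5 | 99% |

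**2. Growth in the control comparison, no device effect.** Noncentral t with 18 degrees of freedom and noncentrality d / √(1/10 + 1/10), where d is now the excess growth in the device group, that is, rate × extra months.

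| Rate (SD per month) | Extra months | d | False-positive rate |
|---|---|---|---|
| any | 0 | 0 | 5% |
| 0.2 | 1 | 0.2 | 7% |
| 0.2 | 2 | 0.4 | 13.5% |
| 0.4 | 1 | 0.4 | 13.5% |
| 0.4 | 2 | 0.8 | 39.5% |

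The extra months apply only if the age ranges lead to a real difference in interval, which the documents do not settle.

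**3. Over-correction.** Take a 4 mm cleft nostril height and 5 mm on the other side. Moving to 6.5 mm gives a raw change of 6.5 − 4 = +2.5 mm. Asymmetry goes from |4 − 5| = 1.0 to |6.5 − 5| = 1.5 mm, so it worsens by 0.5 mm. On the log ratio, |ln(4/5)| = 0.223 becomes |ln(6.5/5)| = 0.262, which is also worse.

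**4. Ratio or difference.** Let both sides grow by 25%: 4 becomes 5 mm and 5 becomes 6.25 mm. Raw change is +1.0 mm. The difference grows from 1.0 to 1.25 mm. The ratio stays at 4/5 = 5/6.25 = 0.80. Only the ratio is unaffected by proportional growth.

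**5. Angle read from one fixed side.** With share p of infants on the commoner side and true correction δ in every infant, the mean signed change is (2p − 1) × δ. For δ = 10 degrees at 7/3 this is 0.4 × 10 = 4 degrees. Power is from 100,000 simulated trials of 10 infants with fixed splits.

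| Split | Mean, δ = 10 (SD 8) | Paired power | Mean, δ = 5 (SD 5) | Paired power |
|---|---|---|---|---|
| 10/0, or side-coded | 10 | 94% | 5 | 80% |
| 8/2 | 6 | 24% | 3 | 20% |
| 7/3 | 4 | 6% | 2 | 6% |
| 6/4 | 2 | 1% | 1 | 2% |
| 5/5 | 0 | 0.2% | 0 | 0.7% |

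Controls do not repair this. With zero mean change in 10 controls, power for 10 degrees (SD 8) falls from 75% to 20% at 8/2 and 7% at 7/3. If the evaluator measures relative to the cleft side, none of this loss occurs.

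**The case against.** The strongest reply is that the plan has an untreated control group photographed at the same two stages, so growth common to both groups drops out. That stands. A reader might infer that growth in general is credited to the device; the documents support this only for nostril height, and only in the paired test or where age and interval differ between groups.

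A reader might also infer that left and right clefts will cancel on the angle. The plan does not say the angle is read from a fixed side, so this is a gap in specification and not a demonstrated error. But nothing written requires the safe convention.

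Over-correction is likewise only a possibility: no section says that it occurs or how often. Nor is it right that the outcomes fail to address the stated Purpose. That section asks whether the system changes soft tissue position, and change is what is measured. The more anatomical position comes from a general sentence in Background Information.

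Finally, the plan leaves room for ratios. Because this is optional, undefined and attached to no outcome, the choice could be made after the data are seen. It does not close the gap.

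**Conclusion.** The point holds as a gap in the definition of the primary outcomes. The paired test on raw nostril height cannot separate growth from device effect. With no effect at all, assumed growth of 0.5 to 1.5 SD gives 29% to 99% significant results; for width, growth works the other way. The control comparison keeps its 5% error rate if growth is equal in both groups, and rises to between 7% and about 40% under the assumed one to two months of extra growth. Raw change cannot distinguish correction from over-correction, and the angle loses most of its power if it is read from a fixed side with mixed clefts.

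All these figures are illustrative. They do not show that the trial's result will be wrong, only that the present wording leaves it open to these readings.

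**What to change.** In Primary Outcome Measures:

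- Define nostril width and height as the cleft/non-cleft ratio in the same photograph, with 1 as the target and benefit scored as movement towards 1, for example as reduction in the absolute log ratio. Use a ratio and not a millimetre difference, which still grows with proportional growth.
- Define the columellar angle as signed deviation from the facial midline, coded relative to the cleft side, with 0 as the target. Overshoot then appears as a change of sign, and the upward bias of an absolute value near zero is avoided.
- State the favourable direction for all four outcomes, including cleft lip width.
- Keep raw values as descriptive.

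In Study Procedures, replace the optional wording on ratios with these definitions, and apply them to control photographs too.

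The cost is small: outcome wording, and measuring the second nostril on views already required. The second reading adds its own measurement error, and the ratio removes growth only so far as both sides grow in proportion. An absolute log ratio is also biased upward near its target, so the signed log ratio should be reported beside it.

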### **Secondary Outcome Measures:**

- Quality of life assessment utilizing an Infant and New Parent Quality of Life questionnaire
  - Time points: initial time of examination with study team, time of surgery

## **Study Design**

Newborns with incomplete cleft lip and parents that consent to presurgical intervention of DynaCleft® + Nasal Elevator system will be compared to a retrospective group of infants born with incomplete cleft lip treated by the UTHealth Texas Cleft-Craniofacial Team that have received surgical intervention and have existing presurgical photographs available for examination. The primary outcome will be to compare craniofacial soft tissue changes measured from extraoral clinical photographs obtained at the initial examination to the ones obtained prior to surgery. The child's guardian who completed the DynaCleft® therapy will also be asked to complete an infant quality of life assessment survey.

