### **Data and Safety Monitoring**

- There are no adverse events expected as there is no direct risk involved with the participants. All patient information will be unidentifiable and stored in password protected devices.
- The DynaCleft® + Nasal Elevator system is an FDA approved medical device. Adverse events can include skin irritation from the adhesive tape. In the event of skin irritation, parents will be offered suggestions to limit irritation (including use of duoderm as a barrier between the skin and tape) or will be allowed to terminate their participation in the study.
- Unanticipated problems will be reported to the Center for the Protection of Human Subjects.
- Periodic assessment of research progression and data collection will be reviewed within the pediatric dental department through presentations and research committee meetings. Any deviations from protocol will be addressed with the research committee and appropriate authorities as necessary.

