## **Ethics**

- IRB approval will not need to be sought from another IRB.
- The prospective aspect of this study will include a request for consent while the retrospective aspect will require a waiver of consent. To protect the privacy of participants, charts will only be accessed with a protected password on encrypted computers within a secure network, participants will be unidentifiable, any data stored will be on an encrypted computer, and individual information will solely be used for the purpose of this study.
- No risks to the safety of the patient or parent/guardian are anticipated with participation in this study. There is potential risk associated with the DynaCleft® + Nasal Elevator system, including skin irritation/allergy to the adhesive used in the system. If a skin allergy is encountered, participation in the study will be discontinued and appropriate care given. There is potential risk of breach of confidentiality with participation in this study, though all personal identifiers will be removed. Additionally, there is the risk that participants may tire or lose interest while completing the DynaCleft® + Nasal Elevator protocol.

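### The quality-of-life analysis set is stated inconsistently and, as worded in Purpose, limited to families who complete the study, which is likely though not certain to flatter the device

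*Combined protocol and SAP*

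**What the plan says.** The combined protocol and SAP describes the quality-of-life population in several places.

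- **Purpose** gives the only statement of who is analysed: "Analyze the effect on quality of life for families that complete the prospective DynaCleft® study".
- **Study Design** (opening paragraph) ties the survey itself to completion of therapy: the child's "guardian who completed the DynaCleft® therapy will also be asked to complete an infant quality of life assessment survey".
- **Study Design, Prospective** is wider and covers the initial and final visits: "The parents of infants enrolled in the DynaCleft® study will be asked to complete an Infant and New Parent Quality of Life survey".
- **Study Procedures, Prospective** sets no completion condition on the survey: "Parents will be asked to complete the Infant and New Parent Quality of Life questionnaire at both the initial visit and date of surgery". The same section has a qualifying rule: "Participants will be required to receive DynaCleft® treatment for at least 2 months before lip surgery to qualify". It also lets parents who decline the device answer the survey at surgery.
- **Secondary Outcome Measures** lists the questionnaire and two time points but names no population.
- **Statistics** plans a paired t-test of within-patient change and 10 enrolled infants. It gives no quality-of-life analysis set, no rule for families who stop early and no missing-data method.

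On leaving early, Data and Safety Monitoring says that parents whose infant has skin irritation may be offered measures to limit it or "will be allowed to terminate their participation in the study". Ethics says that a skin allergy ends study participation, and that "there is the risk that participants may tire or lose interest while completing the DynaCleft® + Nasal Elevator protocol".

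**The concern.** Completing the study or the therapy happens after the device is started and may be affected by it. The reasons for leaving that the protocol names are largely burdens of the device, and a questionnaire on infant and parent quality of life should be sensitive to such burdens. If families who leave for those reasons are dropped, the remaining families may report a better change than all families who began.

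The secondary objective concerns infants who underwent DynaCleft and their families. With 10 enrolled, each lost family is a tenth of the sample. Because the sections disagree, two analysts following the document could also choose different analysis sets after seeing the data.

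**Working it through.** **1. Which text governs.** Purpose (analysis of study completers) and Study Design (survey of therapy completers) point one way. The prospective part of Study Design (survey of enrolled families) and Study Procedures (survey of parents at both time points) point the other way for collection. Wider collection does not by itself widen the analysis: Purpose is the only sentence that says who is analysed, and Statistics does not replace it.

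**2. What happens to a family that stops.** A family leaving over irritation leaves the study, and an allergy also ends study participation. A family with less than 2 months of treatment does not qualify, though the text does not say for what. Nothing provides for a final survey from such families. A paired change needs both surveys, so they drop out of the analysis even under the wider collection text.

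**3. Size of the selection effect.** There is no figure in the plan to reproduce: it gives no stopping rate, quality-of-life SD, effect size or power. Let *d* be the fraction stopping, *C* the mean change in completers and *S* the mean change in those who stop, with positive values meaning improvement.

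- All-enrolled mean = (1 − d)·C + d·S
- Completer mean − all-enrolled mean = C − [(1 − d)·C + d·S] = d·(C − S)

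The only input from the protocol is 10 enrolled. The number stopping and the gap C − S (in SDs of the change) are assumptions.

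| Stop, of 10 | Gap 0.5 SD | Gap 1 SD | Gap 1.5 SD |
|---|---|---|---|
| 1 (d = 0.1) | 0.05 | 0.10 | 0.15 |
| 2 (d = 0.2) | 0.10 | 0.20 | 0.30 |
| 3 (d = 0.3) | 0.15 | 0.30 | 0.45 |

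If C = S, every entry is 0.

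**4. Effect on the planned test.** The paired t-test was simulated with 10 enrolled, a true mean change of 0, SD 1 and two-sided 0.05 (sidedness is not stated, so this is assumed). The families with the worst score on a stopping variable were removed. That variable had correlation ρ with a worse quality-of-life change. The table gives the rate of falsely favourable significant results.

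| Stop, of 10 | ρ = 0 | ρ = 0.3 | ρ = 0.6 |
|---|---|---|---|
| 1 | 2.6% | 3.5% | 5.2% |
| 2 | 2.6% | 4.4% | 7.7% |
| 3 | 2.6% | 5.3% | 11.0% |

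The nominal rate in one direction is 2.5%.

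**5. Scale.** The standard error of a mean change with 10 families is 1/√10 = 0.32 SD. The change detectable with 80% power is about 1.0 SD. In most of the scenarios in step 3, the distortion is below one standard error.

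**The case against.** The best case on the other side is that this is loose wording, not a chosen analysis set. Read literally, the Study Design sentence cannot apply to the survey at the initial visit, since nobody has completed therapy by then. It may simply label the prospective group as opposed to the chart-review controls. Purpose speaks of completing the study, not the therapy, so a family that stopped the device but answered at surgery might still count. Statistics fixes no set at all.

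Much of this stands. A reader might infer that the protocol firmly defines the quality-of-life population as completers of therapy. It does not: the text is inconsistent, and Purpose and Study Design use different conditions. But the charitable reading does not close the gap. The irritation and allergy provisions concern participation in the study, not only use of the device, and no final survey is arranged for those who leave.

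Three further inferences are tempting and not supported:

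- **That the result is biased in the device's favour.** The direction follows from the named reasons for leaving, but it is not shown. Losing interest need not mean that quality of life was harmed.
- **That the plan expects families to stop.** Ethics names a risk, and Data and Safety Monitoring describes an option. Neither predicts stopping.
- **That the secondary objective clearly asks about all starters.** Its wording, infants who underwent the treatment, can be read as starters or completers.

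It is also fair to say that the SD figures are products of assumed inputs, that this is a secondary outcome in a pilot, and that the paired change has no matched control, because non-users are surveyed only at surgery. That last point is a separate weakness, which changing the analysis set would not cure.

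**Conclusion.** The concern holds in a limited form. Following Purpose as written, the quality-of-life analysis selects on an event that device-related problems may cause, and other sections contradict it on who is surveyed. A completers-only result is likely, though not certain, to be more favourable than the result for all families who start. There is no bias if stopping is unrelated to quality of life.

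The size cannot be derived from the documents. Overstatement of 0.1 to 0.3 SD rests on two assumptions: 1 to 3 of 10 families stopping, and a change 1 SD worse among them. This is modest against the sampling error at this sample size, but it is systematic. It is worth correcting because the remedy is cheap.

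**What to change.** - Reconcile Purpose, Study Design (opening paragraph and prospective part) and Study Procedures so that the main quality-of-life analysis set is all families enrolled in the prospective group. Repeat that definition in Statistics.
- State that the 2-month qualifying rule does not remove families from that set.
- Ask families who stop the device, with their agreement, to complete the date-of-surgery survey. Provide for this where the text now ends participation.
- Report the number of families who stop and their reasons.
- Show completers as a supportive analysis.

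**Cost:** wording changes, plus a questionnaire at a surgery visit that takes place anyway. Study Procedures already lets families who never used the device answer at that point, so asking families who started and stopped should be feasible. The downside is that some families who stop may not respond, so the set may still be incomplete. None of this alters clinical care.
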